Similarly, in the RAINBOW trial, which is the largest second-line trial in GC, the addition of ramucirumab to weekly paclitaxel significantly prolonged either median OS (9.6 vs 7.4 months, HR=0.807, p=0.017) or PFS (4.4 vs 2.9 months, HR=0.635, p<0.0001) when compared with paclitaxel monotherapy in 665 patients[17]. A decrease in the risk of death by 19% was seen and a significantly greater proportion of patients attained an objective response in the combination group than in the single-agent group (28% vs 16%, p=0.0001). These results are noteworthy especially in the light of poor risk feature of patients enrolled as demonstrated by the rate of peritoneal metastases higher than 40% in both the experimental and control arms. In a preplanned subgroup analysis, Asian patients derived less survival benefit than non-Asian. A dilution effect by poststudy discontinuation treatment as well as difference in pharmacokinetics has been advocated to explain this discrepant outcome. Interestingly, the survival benefit was achieved while maintaining patient quality of life, delaying symptom worsening and functional status deterioration[24]. The toxicity of ramucirumab was tolerable and, as expected, higher in the combination regimen. In the single-agent trial the most common AE was an increased risk of grade 3 or higher hypertension (8% vs 3%), while when combined with paclitaxel, ramucirumab resulted in significantly increased rates of grade 3-4 neutropenia (40.7% vs 18.8%), though this did not translate into higher incidence of febrile neutropenia. Antiangiogenic class side effects such as proteinuria, bleeding and gastrointestinal perforations were mainly infrequent, mild in grade and more commonly noted in the combination arm.

Thirdline and later lines of therapy

Until recently, no randomized trials with cytotoxics were available to show a survival benefit in 3L+ patients with mGAC. The TAGS trial was a global phase 3 study of adult patients with mGC who had received \geq 2 prior regimens of chemotherapy. Patients were randomized 2:1 to receive FTD/TPI (35 mg/m2 BID on days 1–5 and 8–12 of each 28-day cycle) or placebo, plus best supportive care. Median overall survival was 5·7 months (95% CI 4·8-6·2) in the trifluridine/tipiracil group and 3·6 months (3·1-4·1) in the placebo group (hazard ratio 0·69 [95% CI 0·56-0·85]; one-sided p=0·00029, two-sided p=0·00058)[25].

Immunotherapy Experience with Pembrolizumab

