The combination of pembrolizumab (Keytruda) and cabozantinib (Cabometyx) has antitumor activity in patients with previously treated metastatic renal cell carcinoma (RCC) and is tolerated at their separate approved doses for this indication, based on the findings from a dose-escalation cohort of a phase I study[34]. Among 8 patients enrolled with RCC of any histology, the best objective response was a partial response in 2 patients and stable disease in 4 patients; 2 patients experienced progressive disease. The maximum-tolerated dose (MTD) was identified as 60 mg of oral cabozantinib daily plus 200 mg of pembrolizumab intravenously every 3 weeks. No dose-limiting toxicities (DLTs) were observed with cabozantinib at 40 mg when used in combination with pembrolizumab in patients evaluable for DLT. One patient required a dose reduction from 60 mg of cabozantinib to 40 mg after cycle 5.

Eligible patients in the phase I study (NCT03149822) had documented RCC of any histology, measurable or evaluable disease based on RECIST v1.1 criteria, adequate organ function, and an ECOG performance status of 0 or 1. Patients received pembrolizumab and cabozantinib in a standard 3+3 dose escalation to determine the DLT, MTD, and objective response rate. Cabozantinib was dosed at 40 mg and 60 mg daily in the first and second cohorts, respectively. Pembrolizumab was dosed at 200 mg every 3 weeks in all cohorts. The original study design included only pretreated patients

but after cabozantinib was approved in the first-line setting in patients with intermediateand poor-risk disease, the protocol permitted patients with newly diagnosed metastatic RCC.

The DLT assessment window was 21 days; dose-escalation patients who did not complete the DLT assessment window for any reason other than a DLT were considered non-evaluable for DLT and were replaced. Scans were obtained every 9 weeks, and treatment could continue beyond progression. Two patients in the cabozantinib 40-mg cohort were not evaluable for DLT due to nonadherence and were therefore replaced with 3 patients who were treated at the 60-mg dose.

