2.3 Endpoints

The primary endpoint is 6 months progression-free survival (PFS-6). The secondary endpoints are rates of drug-related grade 3-5 adverse events experienced during and up to four weeks after completion of study treatment. These will be assessed via NCI's CTCAE v5.0 toxicity criteria. Other secondary endpoints are best objective response rate by RECIST v1.1 in patients with measurable disease and overall survival.

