3.0 PATIENT ELIGIBILITY

3.1 Inclusion Criteria

- 3.1.1 Patients must have histologically or cytologically confirmed gastric or gastroesophageal adenocarcinoma
- 3.1.2 Must have locally advanced, recurrent, or metastatic disease not amenable to curative intent surgery.
- 3.1.3 Must have progressed, or not tolerated, at least one line of treatment with a platinum and/or fluoropyrimidine containing regimen. At least one cycle of combination chemotherapy including a platinum (oxaliplatin, cisplatin, carboplatin) and/or fluoropyrimidine (capecitabine or 5-Fluorouracil) based regimen for advanced disease. Combination regimens with platinum/fluoropyrimidine containing a taxane and or a checkpoint inhibitor are allowed. Patients progressing within six months of perioperative chemotherapy or definitive chemoradiation for localized disease are eligible. Patients who have exhausted all other standard of care options are also eligible.
- 3.1.4 Must have received and progressed on one previous line of treatment containing a checkpoint inhibitor (if PD-L1 CPS score unknown or ≥ 10%). Patients with PD-

- L1 CPS score < 10% are eligible independent of whether they have received previous checkpoint inhibitors.
- 3.1.5 Age ≥ 18 years.

Because no dosing or adverse event data are currently available on the use of cabozantinib in patients <18 years of age, children are excluded from this study but will be eligible for future pediatric single-agent trials, if applicable.

- 3.1.6 Performance status: ECOG performance status ≤2 (Appendix A).
- 3.1.7 Life expectancy of greater than 3 months
- 3.1.8 Adequate organ and marrow function as defined below:

Leukocytes	≥ 2,000/mcL
absolute neutrophil count	≥ 1000/mcL
platelets	≥ 60,000/mcl
total bilirubin	within normal institutional limits (or <3mg/dL in patients with Gilbert's disease)
AST(SGOT)/ALT(SPGT)	≤ 3 X institutional upper limit of normal or ≤ 5 X if liver metastases are present
creatinine	< 1.5 X upper limit of normal
hemoglobin	≥ 8 g/dL
Serum albumin	≥ 2.8 g/dL
Urine protein/creatinine ration (UPCR)	≤ 1 mg/mg

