6.1.1 Definitions

Evaluable: All patients receiving cycle 1, day 1 of the protocol treatment.

Evaluable for toxicity. All patients will be evaluable for toxicity from the time of their first treatment with study drug.

Evaluable for objective response. Only those patients who have measurable disease present at baseline, have received at least one cycle of therapy, and have had their disease re-evaluated will be considered evaluable for response. These patients will have their response classified according to the definitions stated below. (Note: Patients who exhibit objective disease progression prior to the end of cycle 1 will also be considered evaluable.)

Evaluable Non-Target Disease Response. Patients who have lesions present at baseline that are evaluable but do not meet the definitions of measurable disease, have received at least one cycle of therapy, and have had their disease re-evaluated will be considered evaluable for non-target disease. The response assessment is based on the presence, absence, or unequivocal progression of the lesions.

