9.0 STATISTICAL CONSIDERATIONS

9.1 Study Design/Study Endpoints

This is a single-arm, open label, phase-II trial designed as a pilot to see if the treatment regimen is worthy of further study. Specifically, the trial is designed as the first stage of a Simon two-stage, minimax design[39]. The goal is to gather evidence on efficacy or futility of the study treatment in this study population, while monitoring toxicity. The two-stage approach offers economy and exposes the fewest possible participants to potential harm without substantial benefit, with control of the probability of errors in decisions.

Primary Endpoint: For efficacy the primary endpoint is progression-free survival at six months (PFS-6), dating from the first dose of study treatment. Progression is defined and determined as given in Section 61.6. For toxicity, the primary endpoint is the number of participants showing serious toxicity during their participation in the trial. Serious toxicities are given in Section 7.0.

Efficacy Null Hypothesis: Based on current outcomes for this study population[25][26], the null hypothesis is that 5% of evaluable patients will be progression-free at six months.

Efficacy Alternative Hypothesis: Based on our clinical judgment and aspirations, we anticipate that 20% (or more) of evaluable participants will be progression-free at six months. In our view, 20% progression-free at six months is the smallest advance that would be judged clinically worthwhile.

Secondary endpoints:

- Overall survival, defined as time from starting treatment to death from any cause.
- Objective response rate in patients with measurable disease as defined in section 6.0
- Safety as described in the adverse events in section 7.0

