9.2 Sample Size and Accrual

Sample Size: Given null- and alternative-hypothesis proportions of 0.05 and 0.20, respectively, approximately 20 evaluable subjects will signal futility/efficacy with 80-percent power and five percent risk of type-I error. Under these conditions the table below gives the number of evaluable subjects required, the smallest number of patients progression-free at six months to signal efficacy, and the probability of correctly declaring futility.

Design Approach	Sample Size	Responses Signal Efficacy	Probability Correctly Asserting Futility
Minimax	19	>=2	0.75

As may be seen, the minimax approach requires 19 evaluable subjects for this project. If at least two participants are progression-free at six months, then the treatment regimen is considered worthy of further study. Given that result, then, in a separate study to complete stage two of the design, an additional eight evaluable subjects would be run. If at least four of the total of 27 evaluable were progression-free at six months that would be sufficient evidence to reject the null hypothesis of five percent in favor of the alternative hypothesis of 20 percent. The probability of declaring futility when in fact the null hypothesis (viz., 5%) is true is at least 75 percent.

No more than nine patients with PD-L1 CPS = 1-9% who are immunotherapy naïve will be enrolled.

Continuous Monitoring for Excess Toxicity: All participants in trial are monitored for serious toxicity for the duration of their participation in the study. Serious toxicities are given in Section 7. A sequential Pocock-type boundary will inform decisions to continue or stop accrual for excess toxicity, as accrual proceeds (Ivanova, 2005). The table below shows the cumulative number of participants enrolled and the corresponding cumulative number of serious toxicities that will signal the underlying risk of serious toxicity exceeds 33 percent (5% risk of type-1 error).

Threshold Number of Cumulative Toxicities that Signal Excess Toxicity as a Function of Cumulative Number Enrolled*

Cumulative	Threshold Number
Number	Showing Serious
Enrolled	Toxicity to Stop
	Accrual
1	-
2	-
3	-

CONFIDENTIAL

4	4
5	5
6	5
7	6
8	7
9	7
10	7
11	8
12	8
13	9
14	9
15	10
16	10
17	11
18	11
19	12
20	12

^{*} Pocock -type boundary with maximum acceptable probability of toxicity set to 33 percent and type-1 risk of five percent[40].

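### Eligibility does not require a lesion on baseline imaging, yet every dosed patient counts in PFS-6; where no lesion is visible, progression may be registered later and more subjectively.

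*Combined protocol and SAP*

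**What the plan says.** **Eligibility.** Criterion 3.1.1 asks for histologic or cytologic confirmation. On extent of disease, 3.1.2 reads: "Must have locally advanced, recurrent, or metastatic disease not amenable to curative intent surgery". None of 3.1.1 to 3.1.12 asks for measurable disease, or for non-measurable but evaluable disease, and the exclusions in Section 3.2 do not supply the condition. Sections 5.1.15 and 5.5 require baseline imaging, but do not require that it show a lesion.

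**Who counts.** Section 6.1.1 defines evaluable as "All patients receiving cycle 1, day 1 of the protocol treatment". Section 9.1 states both hypotheses on that group: "the null hypothesis is that 5% of evaluable patients will be progression-free at six months" and "we anticipate that 20% (or more) of evaluable participants will be progression-free at six months". Section 4.9 rules out replacement. Measurable disease limits only the response endpoint, which Section 2.3 gives as "best objective response rate by RECIST v1.1 in patients with measurable disease".

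**What counts as progression.** Section 6.1.6 counts death, radiographic progression, and clinical deterioration that the investigator attributes to the disease. Sections 6.1.4.2 and 6.1.4.3 treat any new lesion as progressive disease. Scans are every 8 weeks in the first year (Section 5.3.3).

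**Comparison within the protocol.** Section 1.3 reports that the phase I trial of the same combination in renal cell carcinoma required "measurable or evaluable disease based on RECIST v1.1 criteria".

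**The concern.** Radiographic progression is normally found in one of two ways: known lesions grow, or new ones appear. A patient with no lesion on the baseline scan has only the second. The 8-weekly scan then cannot show that existing disease is growing. What remains is a new lesion, clinical judgement in an unblinded trial, or death.

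If those events are recorded later than lesion growth would have been, some patients whose disease has advanced will be scored progression-free at six months. The error favours the treatment, and there is no control arm in which it would also occur. PFS-6 is compared with a fixed 5%, and the cut-offs are small counts: 2 of 19 to continue and 4 of 27 to reject the null. At such counts a single patient can decide the outcome.

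The lesion-based classifications in Sections 6.1.1 and 6.1.4.3 cover patients with target lesions and patients with non-target lesions. They do not say how to classify a patient with neither.

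**Working it through.** **Inputs.** Sections 9.1 and 9.2 give the null rate 0.05, the alternative 0.20, stage 1 of 19 (continue if at least 2 are progression-free), 8 more patients, and rejection if at least 4 of 27. The stated targets are: "approximately 20 evaluable subjects will signal futility/efficacy with 80-percent power and five percent risk of type-I error". Section 9.2 also gives a 0.75 probability of correctly declaring futility.

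**Step 1: reproduce the design.** Let X1 be the number progression-free among the first 19 and X2 the number among the next 8.

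P(reject) = sum over x ≥ 2 of P(X1 = x) × P(X2 ≥ 4 − x)

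At 0.05:
- x = 2: 0.1787 × 0.0572 = 0.0102
- x = 3: 0.0533 × 0.3366 = 0.0179
- x ≥ 4: 0.0132
- total, with unrounded terms: 0.0414

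The probability of stopping after stage 1 under the null is 0.755, so the chance of passing is 0.245. At 0.20 the same formula gives power 0.803. The stated design reproduces.

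**Step 2: add patients with no visible baseline lesion.** Let k of the 27 be such patients, each with chance q of being scored progression-free under the null, placed at random across the two stages. All others stay at 0.05. Neither k nor q is in the documents; both are assumptions.

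Worked case, k = 1 and q = 0.30:
- In stage 1 (probability 19/27), the chance of passing stage 1 is 0.30 × P(at least 1 of 18) + 0.70 × P(at least 2 of 18) = 0.30 × 0.6028 + 0.70 × 0.2265 = 0.339. The type I error is 0.0664.
- In stage 2 (probability 8/27), the chance of passing stage 1 stays 0.245. The type I error is 0.0622.
- Average type I error: (19/27) × 0.0664 + (8/27) × 0.0622 = 0.0652.
- Average chance of passing stage 1: (19/27) × 0.339 + (8/27) × 0.245 = 0.311.

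The same enumeration over a range of q gives:

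| q | Type I error, k = 1 | Type I error, k = 2 |
|---|---|---|
| no such patients | 4.1% | 4.1% |
| 0.10 | 4.6% | 5.1% |
| 0.20 | 5.6% | 7.3% |
| 0.30 | 6.5% | 9.7% |
| 0.50 | 8.4% | 15.4% |

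With one such patient the error reaches 5.0% at about q = 0.14.

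**Step 3: the alternative reading of the null.** Suppose 5% is the average over all dosed patients, including those with no visible lesion. With k = 1 and q = 0.30 the other 26 must then have rate (27 × 0.05 − 0.30)/26 = 1.05/26 = 0.040. The type I error becomes 3.7%, slightly below 4.1%. On this reading nothing is inflated.

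**The case against.** **Progression is not invisible in these patients.** A reader might infer that they pass because progression cannot be seen at all. The documents do not support that. New lesions, clinical deterioration and death all count, and both tables in Section 6.1.4.3 score a new lesion as progression whatever the other findings. PFS under Section 6.1.6 does not depend on a baseline lesion. This objection stands in full: the loss is confined to radiographic follow-up of existing disease.

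**The frequency is unknown.** Section 1.1 mentions, for one second-line trial, a "rate of peritoneal metastases higher than 40% in both the experimental and control arms". It is tempting to read this as evidence that image-negative patients are common. The figure covers all peritoneal metastases and says nothing about visibility on CT or MRI, so it supports no value of k. This also stands.

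**The upper values of q may be too high.** Section 9.1 bases the null partly on the third-line trial in Section 1.1, with median survival of 5.7 and 3.6 months. Assuming exponential survival, 0.5^(6/5.7) = 48% and 0.5^(6/3.6) = 32% are alive at six months. In such a population q of 0.30 to 0.50 leaves little or no room for any event except death. Patients treated in earlier lines live longer (9.1 months on pembrolizumab in one second-line trial cited there), so the range is not refuted, but it lies towards the ceiling. The low rows of the table matter for this reason.

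**The null may already include these patients.** Section 9.1 states 5% for evaluable patients, meaning everyone dosed. Step 3 shows that the inflation then disappears. The documents do not show that 5% was derived from a population that included such patients, so both readings stay open.

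**Existing safeguards.** Baseline imaging and tumor measurements are scheduled, and 3.2.27 lets the investigator exclude a patient whose condition might confound the results. These make enrolment of such a patient less likely without ruling it out.

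**Measurable disease need not be required.** That is a legitimate choice for a PFS endpoint, and the change proposed here respects it.

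**Conclusion.** The gap in eligibility is real. As written, the plan admits patients whose existing disease the scans cannot follow and counts them in the primary endpoint. For them, progression may be recorded later and with more reliance on judgement, and the likely direction of bias is upward.

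The size is a sensitivity range and not an estimate. It rests on assumed k and q, on all other patients having a true rate of 5%, and on 5% not already being the rate for the mixed cohort. At q = 0.10 one such patient leaves the error within the nominal 5%; at q = 0.20 or above, one is enough to exceed it. A reader might infer from the table that the trial's type I error is inflated. The documents do not establish that, because they do not show that any such patient would enrol.

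This is an inexpensive improvement to eligibility. It does not invalidate the design, whose stated error limits are met.

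**What to change.** Add one line to Section 3.1: *At least one lesion, measurable or non-measurable but evaluable by RECIST v1.1, on the baseline CT/MRI.*

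This keeps patients with ascites, bone disease or peritoneal disease visible on CT, and does not demand measurable disease. It is checked on a scan that the protocol already requires. The sample size (19 then 27), the cut-offs, the type I error of 4.1% and the power of 80.3% are unchanged, provided the 5% and 20% rates are meant for patients with visible disease. The cost is the exclusion of a small number of patients with image-negative disease.

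If the sponsor prefers to keep those patients, state in Section 6.1 how a patient with no visible baseline lesion is classified for PFS-6, and add to Section 9.3 a sensitivity analysis of PFS-6 without them.

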Study Product(s), Dose, Route, Regimen	Cabozantinib 40 mg p.o. daily days 1-21 Pembrolizumab 200 mg i.v. day 1 every 21 days
Study Duration	The study will consist of a screening period of up to 28 days, a treatment period (21 day cycles), and a follow up period of up to 18 months after enrollment of the last patient or until death, whichever occurs first. Subjects will be allowed to continue treatment on study until disease progression, unacceptable toxicity or withdrawal of consent.
Statistical Methodology	Main objective is to estimate the efficacy of the combination regimen with PFS-6 as a primary endpoint. The null hypothesis in this heavily pretreated population is a PFS-6 of 5%. The alternative hypothesis assumes a PFS-6 of 20% or more. A 2-stage approach will be used. If PFS-6 is seen in at least 2 out of the first 19 patients, the cohort will be expanded to a total of 27 patients. If the PFS-6 is achieved in at least 4 patients in the expanded cohort, that would be sufficient evidence to reject the null hypothesis of 5% in favor of the alternative hypothesis of 20% or more.

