KEYNOTE-059 was a global, open-label, single-arm, multicohort study in patients with 2+ lines of prior treatment[26]. Treatment consisted of pembrolizumab 200mg every 3 weeks. ORR was the primary endpoint and ranged from 6.4% (PD-L1 negative population) to 15.5% (PD-L1 positive population). Median response duration was reported as 16.3 months in patients with PD-L1 positive tumors.

KEYNOTE-061was a global randomized phase 3 trial of single agent pembrolizumab 200mg every 3 weeks vs. standard dose paclitaxel in patients with advanced gastric or gastro-esophageal junction cancer that progressed on first-line chemotherapy with a platinum and fluoropyrimidine[27]. Primary endpoints were overall survival and progression-free survival in patients with a programmed cell death ligand 1 (PD-L1) combined positive score (CPS) of 1 or higher. Median overall survival was 9·1 months (95% CI 6·2-10·7) with pembrolizumab and 8·3 months (7·6-9·0) with paclitaxel (hazard ratio [HR] 0·82, 95% CI 0·66-1·03; one-sided p=0·0421). Median progression-free survival was 1·5 months (95% CI 1·4-2·0) with pembrolizumab and 4·1 months (3·1-4·2) with paclitaxel (HR 1·27, 95% CI 1·03-1·57). In the total population, grade 3-5 treatment-

related adverse events occurred in 42 (14%) of the 294 patients treated with pembrolizumab and 96 (35%) of the 276 patients treated with paclitaxel. Pembrolizumab reduced the risk of death by 18% vs. paclitaxel in patients with previously treated G/GEJ cancer and PD-L1 CPS ≥1, although this difference was not statistically significant. In post-hoc analysis, the pembrolizumab treatment effect for OS was greater for CPS ≥5 (HR 0.73; 95% CI 0.52-1.03) and ≥10 (HR 0.64; 95% CI 0.41-1.02).

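### The 5% PFS-6 null is presented as the current outcome for this study population, but the two cited trials enrolled later-line patients and the only PFS-6 the protocol reports from either is 14.1%

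*Combined protocol and SAP*

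**What the plan says.** Section 9.1 gives the basis for the null: "Based on current outcomes for this study population[25][26], the null hypothesis is that 5% of evaluable patients will be progression-free at six months". The Study Summary puts it this way: "The null hypothesis in this heavily pretreated population is a PFS-6 of 5" percent. The alternative is 20%, and section 9.1 says that "20% progression-free at six months is the smallest advance that would be judged clinically worthwhile". Section 9.2 claims that "approximately 20 evaluable subjects will signal futility/efficacy with 80-percent power and five percent risk of type-I error". The decision rule has two steps. The Study Summary gives the first: "If PFS-6 is seen in at least 2 out of the first 19 patients, the cohort will be expanded to a total of 27 patients". At least four successes among the 27 then reject 5%.

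Reference 25 is the trifluridine/tipiracil trial (TAGS), which section 1.1 describes as enrolling patients after two or more chemotherapy regimens. Of reference 26, section 1.1 says: "KEYNOTE-059 was a global, open-label, single-arm, multicohort study in patients with 2+ lines of prior treatment". Section 1.4 reports a PFS-6 of 14.1% and a median PFS of 2.0 months from that same trial.

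Entry is wider. Under 3.1.3 a patient "Must have progressed, or not tolerated, at least one line of treatment with a platinum and/or fluoropyrimidine containing regimen". The short title says 2L+. The primary objective (2.1.1) speaks of progression on at least one line and does not mention intolerance. No section caps, stratifies or separately analyses patients by number of prior lines. The only cap (9.2) is nine immunotherapy-naive patients with PD-L1 CPS 1-9%.

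**The concern.** A single-arm test borrows its control from history. If the historical rate is lower than the enrolled patients would reach on existing treatment, rejecting it says little about the new regimen. The two sources cited here are later-line trials, while this cohort may contain any share of second-line patients, for whom section 1.1 reports longer PFS on several active regimens. The one PFS-6 figure that can be traced to a cited source is also almost three times the null (14.1 / 5 = 2.8). A positive result could therefore reflect who was enrolled, or a null set too low, rather than activity of the combination. That result decides whether the regimen is called worthy of further study.

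**Working it through.** **1. Reproduce the design.** Inputs from 9.1-9.2: p0 = 0.05, p1 = 0.20, continue if at least 2 of 19, reject if at least 4 of 27. With X successes among the first 19 and Y among the next 8,

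P(reject | p) = P(X=2)·P(Y≥2) + P(X=3)·P(Y≥1) + P(X≥4).

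- At p = 0.05: 0.1787 × 0.0572 + 0.0533 × 0.3366 + 0.0132 = 0.041.
- At p = 0.20: 0.803.
- Probability of stopping at stage 1 under the null, P(X≤1 | 0.05) = 0.755.

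These agree with the stated 5% type I error, 80% power and 0.75 futility probability. The arithmetic of the design is sound for its inputs. The question is the 5%.

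**2. The reported PFS-6 from a cited source.** At p = 0.141: 0.2566 × 0.3143 + 0.2387 × 0.7036 + 0.2752 = 0.52. The chance of passing stage 1 alone is 0.77.

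**3. Second-line benchmarks in section 1.1.** The documents give medians, not PFS-6, for these regimens. Assume exponential PFS, so PFS-6 = 0.5^(6/median). As a check, the 2.0-month median in the pembrolizumab trial gives 12.5%, against the reported 14.1%.

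| Regimen (median PFS, months) | Implied PFS-6 | P(reject 5%) |
|---|---|---|
| Placebo (1.3) | 4.1% | 0.02 |
| Pembrolizumab (1.5) | 6.3% | 0.08 |
| Ramucirumab (2.1) | 13.8% | 0.51 |
| Irinotecan (2.2) | 15.1% | 0.58 |
| Irinotecan (2.8) | 22.6% | 0.88 |
| Paclitaxel (2.9) | 23.8% | 0.90 |
| Paclitaxel (4.1) | 36.3% | 0.995 |
| Ramucirumab plus paclitaxel (4.4) | 38.9% | 0.998 |

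The 2.9 and 4.4 months come from one trial: "PFS (4.4 vs 2.9 months, HR=0.635, p<0.0001) when compared with paclitaxel monotherapy in 665 patients". From 2.8 months upward, the implied PFS-6 already exceeds the 20% target.

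**4. Mixed cohort.** Suppose, for illustration, that half the patients are second-line with rate q and half have 5%, so p = (q + 0.05)/2.

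- q = 6.3% (pembrolizumab): p = 5.6%, P(reject) 0.06
- q = 13.8% (ramucirumab): p = 9.4%, P(reject) 0.24
- q = 23.8% (paclitaxel): p = 14.4%, P(reject) 0.54
- q = 38.9% (ramucirumab plus paclitaxel): p = 21.9%, P(reject) 0.86

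**5. Could the trial test 14.1% instead?** With 27 patients, at least 8 successes would be needed (type I error 0.029), and power at 20% would be 0.16. The present size cannot separate 20% from 14.1%.

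**The case against.** The strongest reply is that the high rejection probabilities come from drugs these patients do not receive. For the one study drug with a second-line median in section 1.1, pembrolizumab, the implied PFS-6 is 6.3% and the rule rejects with probability 0.08. Transfer is also uncertain: this trial admits ECOG 2, the ramucirumab monotherapy trial took ECOG 0-1, and many patients here must already have progressed on a checkpoint inhibitor. This stands as a limit on size. A reader might infer that any ordinary second-line result would be declared a success. The documents do not support that, because the answer depends on the comparator and the mix.

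A sponsor could defend 5% as a rate for checkpoint-refractory disease. The protocol does not make that argument, gives no such figure, and under 3.1.4 admits checkpoint-naive patients with CPS below 10%.

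A reader might also infer that patients can generally enter without having progressed. That goes too far. Section 3.1.4 requires progression on a checkpoint-inhibitor line when CPS is unknown or at least 10%, and 3.1.12 requires progression after immunotherapy for known MSI-High or dMMR tumours. Intolerance without any progression is open mainly to patients with CPS below 10%, and its effect cannot be sized from the documents.

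Finally, section 9.1 calls this a pilot and claims no superiority over second-line treatment. That lowers the severity, but section 9.2 still treats four successes in 27 as grounds to reject 5% in favour of 20%.

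**Conclusion.** The stated basis for the null does not hold as written and should be corrected; the binomial design itself is right for its inputs. Both cited trials required more prior treatment than this one. It is tempting to conclude that 5% is correct for patients with two or more prior regimens and fails only because second-line patients are admitted. The documents do not support that either: their only PFS-6 from such a population is 14.1%, at which the rule rejects 5% about half the time (0.52). They report no PFS for TAGS, so it cannot be judged whether 5% comes from there.

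The 0.52 needs no distributional assumption beyond independent binary outcomes. The second-line range of 0.08 to 0.998 rests on exponential PFS and on carrying other trials' medians over to this cohort. The half-and-half range of 0.06 to 0.86 also rests on an assumed mix. Together they show that case mix could decide the result, not that it will.

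**What to change.** In sections 9.1-9.2, before PFS-6 results are known:

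- Remove the statement that 5% reflects current outcomes for this study population, or give the source and the population for it. Do not assert that it applies to patients with two or more prior regimens.
- Report the rule's rejection probability at 14.1% and at the second-line benchmarks beside the 5% and 20% figures.
- State that rejecting 5% in the mixed cohort does not show improvement over the 14.1% or over the second-line results in section 1.1.
- Pre-specify PFS-6 counts with exact intervals for one versus two or more prior regimens, and for progressed versus intolerant at entry. The oncology history taken under 5.1.3 should supply both.
- Reconcile 2.1.1 (progressed on at least one line) with 3.1.3 (progressed or not tolerated).

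The cost is wording, a short table of operating characteristics and one results table, with no change to eligibility or sample size. The price is small subgroups with wide intervals and a narrower claim.
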